3.0 Introduction

This statistical analysis plan (SAP) describes the statistical analyses to be completed by AbbVie Statistics and Statistical Programming for Study Protocol M14-222.

Study M14-222 (TOPAZ-II) and companion Study M14-423 (TOPAZ-I) are designed together and shares the primary objective of evaluating the effect of treatment response (assessed by the status of SVR₁₂, i.e., HCV ribonucleic acid (RNA) < lower limit of quantification [LLOQ] 12 weeks following treatment) on long-term clinical outcomes in adults with genotype 1 (GT1) chronic hepatitis C virus (HCV) infection who received treatment with ABT-450/r/ABT-267 and ABT-333 with or without ribavirin, as measured by all-cause death, liver-related death, liver decompensation, liver transplantation, and hepatocellular carcinoma.

In the TOPAZ-I and TOPAZ-II studies, the primary objective is to be assessed, based on the data from both studies combined. The studies differ based on geographic region (this study will be conducted in the US while the TOPAZ-I study will be conducted outside the US) and based on certain procedures that are not related to the primary outcome. For example, this study will utilize a Subject Care Plan Model to facilitate subjects' adherence to the study drug and the TOPAZ-II study will assess the long-term change from baseline in liver elastography.

This SAP provides details to guide the analyses for baseline, efficacy, and safety variables and describes the populations and variables that will be analyzed and the statistical methods that will be utilized. An interim analysis (after all subjects reach Post-Treatment [PT] Week 12 or prematurely discontinue the study) and an end of study analysis will be conducted for Study M14-222. Analyses will be performed using SAS[®] Version 9.3 (SAS Institute, Inc., Cary, NC) or later under the UNIX operating system.

4.0 Study Objectives, Design and Procedures

4.1 Objectives

The primary objective of this study is to evaluate the effect of virologic response to treatment (assessed by SVR₁₂ status) on the long-term progression of liver disease in adults with chronic HCV GT1 infection who receive treatment with ABT-450/r/ABT-267 and ABT-333 with or without ribavirin, as measured by all-cause death, liver-related death, liver decompensation, liver transplantation, and hepatocellular carcinoma.

The secondary objectives are to evaluate the sustained virologic response in adults with GT1 chronic HCV infection who receive ABT-450/r/ABT-267 and ABT-333 with or without ribavirin, to assess the change from baseline in quality of life and fatigue following treatment assessed by Short-Form 36 Version 2 health survey (SF-36v2) and the Functional Assessment of Chronic Illness Therapy – Fatigue (FACIT-F) questionnaires, respectively) by baseline fibrosis stage, and to assess adherence to the prescribed regimen (measured by pill counts for each type of tablet). Sustained virologic response is evaluated by the percentage of subjects achieving SVR₁₂.

[figure not shown]
4.2 Design Diagram

Study M14-222 is a Phase 3b, open-label, multi-center study, which is designed together with companion Study M14-423 (TOPAZ-I) to share the primary objective of assessing the effect of treatment response on long-term clinical outcomes in adults with GT1 chronic HCV infection with or without compensated cirrhosis, who are either treatment-naïve or IFN/ribavirin (IFN or peg IFN/RBV) treatment-experienced. Approximately 600 subjects will be enrolled in Study M14-222 at approximately 50 sites in the US. At least 100, but no more than 150 cirrhotic subjects with fibrosis stage of F4 will be allowed to enroll. At least 50, but no more than 110 subjects with fibrosis stage of F3 will be allowed to enroll.

As shown in [Figure 1](#), subjects meeting eligibility criteria will be enrolled to either 12 or 24 weeks of treatment according to HCV subtype and presence of cirrhosis. Subjects

who receive at least one dose of study drug will be followed in the Post-Treatment Period for up to 5 years (PT Week 260).

Figure 1. Study Schematic

The duration of the study will be 272 weeks (for subjects receiving a 12-week treatment) or 284 weeks (for subjects receiving a 24-week treatment), not including a screening period of up to 42 days, consisting of a 12-week or 24-week Treatment Period and a 260-week Post Treatment (PT) Period for all subjects who receive at least one dose of study drug.

Treatment Period

Subjects who meet the eligibility criteria will be enrolled to either 12 or 24 weeks of combination therapy with or without RBV as described in [Table 1](#). All HCV GT1-infected subjects who are either treatment-naïve or treatment-experienced will receive ABT-450/r/ABT-267 150/100/25 mg once daily (QD) and ABT-333 250 mg twice daily (BID). Subjects with HCV GT1a infection and all GT1-infected subjects with compensated cirrhosis will also receive RBV with weight-based dosing 1000 or 1200 mg BID.

The treatment duration will be 12 weeks for all subjects except GT1a-infected subjects with compensated cirrhosis who will receive treatment for 24 weeks unless a treatment duration of 12 weeks is selected by the investigator based on subject's prior treatment history. Subjects will receive study drug regimens according to criteria listed in [Table 1](#).

Upon completing the Treatment Period or premature discontinuation of the Treatment Period, subjects will enter the Post Treatment (PT) Period.

Table 1. Treatment Regimen and Duration

Subject Population	Treatment Regimen*	Treatment Duration
Genotype 1a, without cirrhosis	ABT-450/r/ABT-267 + ABT-333 + RBV	12 weeks
Genotype 1a, with cirrhosis	ABT-450/r/ABT-267 + ABT-333 + RBV	24 weeks**
Genotype 1b, without cirrhosis	ABT-450/r/ABT-267 + ABT-333	12 weeks
Genotype 1b, with cirrhosis	ABT-450/r/ABT-267 + ABT-333 + RBV	12 weeks

* Follow the genotype 1a dosing recommendations in patients with an unknown genotype 1 subtype or with mixed genotype 1 infection.

** Treatment for 12 weeks may be considered for some patients based on prior treatment history.

Post-Treatment Period

Subjects who receive at least one dose of study drug in the Treatment Period and either complete treatment or prematurely discontinue study drug will be followed in the Post-Treatment Period for up to 260 weeks. At the Post-Treatment visits subjects will be monitored for antiviral response, assessment of patient reported outcomes (PROs), and clinical outcomes, including all-cause death, liver-related death, and occurrence of liver decompensation, liver transplantation and hepatocellular carcinoma.

The Post-Treatment Period will begin the day following the last dose of study drug treatment.

4.3 Sample Size

Assuming 4% of subjects do not achieve SVR₁₂ and assuming the 5-year event rate of the composite clinical outcome is 20% in the non-SVR₁₂ subjects, with a 75% reduction in SVR₁₂ subjects (Hazard Ratio of 0.25),^{1,2} then based on two-sample log rank test (using EAST 6.0), a sample size of at least 2000 subjects enrolled in TOPAZ-I (planned to enroll 1650 subjects) and TOPAZ II (planned to enroll 600 subjects) provides greater than 80% power to reject the null hypothesis of no difference between SVR₁₂ and non-SVR₁₂

subjects in the rate of clinical outcome events. Power calculations were based on a dropout rate of up to 20% for the hazard ratio.

4.4 Planned Analysis

The primary analysis to evaluate the effect of response to treatment on clinical outcomes will occur at the final analysis after all subjects have completed the study or prematurely discontinued the study. An interim analysis to assess the percentage of subjects achieving SVR₁₂ will occur after all subjects have completed the Post-Treatment Week 12 Visit or prematurely discontinued the study. For both final and interim analyses, data will be locked after performing appropriate data cleaning. Data after the interim analysis will be added to a subsequent version of the database. SAS[®] (SAS Institute, Inc., Cary, NC) for the UNIX operating system will be used for all analyses. All statistical tests and all confidence intervals will be two-sided with an α level of 0.05.

All analyses will be conducted by statisticians and statistical programmers at AbbVie or the designee according to the methodologies specified in this SAP. There is no intention of shortening the follow-up time of subjects based on efficacy findings from the interim analysis. The intention is to follow all subjects who receive study drug for 260 weeks following treatment. There will be no statistical adjustment employed due to this interim analysis.

5.0 Analysis Populations

5.1 Definition for Analysis Populations

5.1.1 Intent-to-Treat (ITT) Population

The intent-to-treat (ITT) population will consist of all enrolled subjects in this study (ITT-II) and companion study TOPAZ-I (ITT-I) who receive at least one dose of study drug.

The primary efficacy analysis on clinical outcomes will be performed on the ITT population that combines ITT-I and ITT-II.

5.1.2 Intent-to-Treat-II (ITT-II) Population

The ITT-II population will consist of all subjects enrolled in this study who receive at least one dose of study drug. The data from the ITT-II population will be presented in one column for all subjects regardless of treatment duration and RBV use.

All efficacy, patient reported outcomes and resistance analyses, except for the primary efficacy analysis, will be performed on the ITT-II population. In addition, sensitivity analyses of SVR₁₂ will be performed on the Modified Intent-to-Treat-II Genotype (mITT-II-GT) population and Modified Intent-to-Treat-II Genotype and Virologic Failure (mITT-II-GT + VF) population, respectively, as specified in Section 10.6.

5.1.3 Safety Population

All subjects in this study who receive at least one dose of study drug will be included in the safety population. If all subjects take the treatment to which they were assigned, the safety population will be the same as the ITT-II population. Safety analyses will be performed on the safety population and be presented also for all subjects together.

Demographic and safety analyses will be performed on the safety population.

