In summary, the 3-DAA regimen, with or without RBV, was well tolerated with a low discontinuation rate. Adverse events were typically mild, and many of the adverse events and laboratory abnormalities observed were attributable to the presence of RBV. Transient, asymptomatic serum ALT elevations were observed at a low rate, were not associated with hepatic dysfunction and generally resolved with ongoing treatment.

A detailed discussion of the preclinical toxicology, metabolism, pharmacokinetics and drug-drug interactions can be found in the Investigator's Brochure for ABT-267, ABT-450, ABT-333 and product label for ritonavir and ribavirin.²⁵⁻²⁹

The current study is intended to evaluate the long-term outcomes with ABT-450/r/ABT-267 and ABT-333 with or without RBV for treatment-naïve and IFN/RBV treatment-experienced adults with chronic HCV GT1 infection, with or without compensated cirrhosis.

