8.0 Patient Disposition

The number of subjects for each of the following categories will be summarized overall and by each investigator on the safety population.

- Subjects who took at least one dose of study drug;
- Subjects who completed study drug;
- Subjects who discontinued from study drug;
- Subjects who completed the study;
- Subjects ongoing in the Post-Treatment Period at the time of the interim analysis;
- Subjects who discontinued from the study.

The number and percentage of subjects who discontinued study drug will be summarized by reason (all reasons) and by primary reason (per eCRF). Similar summaries will be provided for discontinuations from the study.

The number and percentage of subjects will be summarized for:

- Subjects with interruptions of all study drugs for toxicity management;
- Subjects with any RBV dose modification;
 - Subjects with RBV dose modification due to decrease in hemoglobin;
 - Subjects with RBV dose modification due to decrease in creatinine clearance;
 - Subjects with RBV dose modification due to weight change;
 - Subjects with RBV dose modification due to other reasons;
- Subjects with any RBV dose modification to 0 mg (i.e., RBV interruptions).

Reasons for study drug interruptions and RBV dose modifications will be presented in the CSR listings.

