11.0 Safety Analysis

11.1 General Considerations

All subjects who receive at least one dose of study drug in Study M14-222 will be included in the safety analyses.

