11.2.1.1 Tabulations of Treatment-Emergent Adverse Events

Adverse event data will be summarized and presented using primary MedDRA system organ classes (SOCs) and preferred terms (PTs) according to the version of the MedDRA coding dictionary used for the study at the time of database lock. The actual version of the MedDRA coding dictionary used will be noted in the clinical study report. The system organ classes will be presented in alphabetical order and the preferred terms will be presented in alphabetical order within each system organ class.

Adverse Event Overview

An overview of adverse events will be presented consisting of the number and percentage of subjects experiencing at least one event for the following adverse event categories:

- Any treatment-emergent adverse event;

- Treatment-emergent adverse events with a "reasonable possibility" of being related to DAAs;
- Severe treatment-emergent adverse events;
- Serious treatment-emergent adverse events;
- Treatment-emergent adverse events leading to discontinuation of study drug;
- Treatment-emergent adverse events leading to interruption of study drug;
- Treatment-emergent adverse events leading to RBV dose modifications;
- Treatment-emergent adverse events leading to death;
- Deaths.

Adverse Event by SOC and PT

The following summaries of adverse events will be generated:

- Treatment-emergent adverse events;
- Treatment-emergent adverse events with a "reasonable possibility" of being related to DAAs;
- Serious treatment-emergent adverse events;
- Moderate or severe treatment-emergent adverse events;
- Severe treatment-emergent adverse events;
- Grade 3 or 4 (see definition below) treatment-emergent adverse events;
- Treatment-emergent adverse events leading to discontinuation of study drug;
- Treatment-emergent adverse events leading to interruption of study drug;
- Treatment-emergent adverse events leading to RBV dose modifications;
- Treatment-emergent adverse events leading to death;
- Treatment-emergent adverse events leading to concomitant medication use (events with other action taken of "concomitant medication prescribed").

For all adverse event summaries, the number and percentage of subjects experiencing treatment-emergent adverse events will be tabulated according to SOC and PT. Subjects reporting more than one adverse event for a given PT will be counted only once for that

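### The SAP plans no safety table by regimen or ribavirin use and does not restrict ribavirin dose-modification percentages to subjects who received ribavirin

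*SAP*

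**What the plan says.** SAP 4.2 and SAP Table 1 define three regimens, writing 3-DAA for ABT-450/r/ABT-267 plus ABT-333.

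- On RBV: "Subjects with HCV GT1a infection and all GT1-infected subjects with compensated cirrhosis will also receive RBV". GT1b subjects without cirrhosis are therefore the RBV-free group.
- On duration: "The treatment duration will be 12 weeks for all subjects except GT1a-infected subjects with compensated cirrhosis who will receive treatment for 24 weeks", unless the investigator selects 12 weeks on treatment history.

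The regimens are thus 3-DAA for 12 weeks, 3-DAA + RBV for 12 weeks, and 3-DAA + RBV for 24 weeks.

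For display, SAP 5.1.2 has the ITT-II data "presented in one column for all subjects regardless of treatment duration and RBV use". SAP 5.1.3 follows with "Safety analyses will be performed on the safety population and be presented also for all subjects together", and SAP 11.1 adds: "All subjects who receive at least one dose of study drug in Study M14-222 will be included in the safety analyses". Nothing later in Section 11 splits adverse events, laboratory values or vital signs by regimen, RBV use, cirrhosis or duration.

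Two places report RBV dose changes as a number and percentage. SAP 8.0 lists "Subjects with any RBV dose modification", with reasons and interruptions beneath it. SAP 11.2.1.1 lists "Treatment-emergent adverse events leading to RBV dose modifications", both in the overview and by system organ class and preferred term.

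Splits do exist elsewhere. Section 7 splits baseline, medical-history and medication tables by cirrhosis and subtype. Section 9.1 gives exposure categories by planned duration, Section 9.2 reports RBV compliance separately, and Section 10.5 gives SVR12 subgroups. None of these shows toxicity.

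**The concern.** A percentage of subjects whose RBV dose was changed is informative only among subjects who took RBV. Adding subjects who cannot have the event lowers the figure by an amount that depends on the enrolment mix and has nothing to do with tolerability.

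The wider point concerns RBV-driven toxicity. The protocol's Introduction concludes that "many of the adverse events and laboratory abnormalities observed were attributable to the presence of RBV", and its Table 3 bears this out for anemia: hemoglobin below 10 g/dL was 0% without RBV, 5.5%, 6.2% and 7.2% in the three 12-week RBV groups, and 11.0% at 24 weeks. One pooled column mixes these rates into a number that describes none of the regimens. The current protocol assigns 24 weeks with RBV by default to all GT1a subjects with cirrhosis, yet no planned toxicity table isolates them.

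Attribution does not fill the gap. Protocol 6.3 collects relationship to DAAs and to RBV, while SAP 11.2.1.1 tabulates relationship to DAAs only.

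**Working it through.** The plan states no figure for the RBV-free share, so there is none to reproduce. One related protocol figure can be checked. The Introduction gives 6% for hemoglobin below 10 g/dL in non-cirrhotic subjects on RBV for 12 weeks. From Table 3, (5.5% × 765 + 6.2% × 401) / 1,166 = 5.74%, which agrees.

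**Inputs**
- N = 600, with 100 to 150 subjects at F4 (SAP 4.2).
- GT1b share b among non-cirrhotic subjects: assumed. The protocol's Introduction reports 32.3% (Study M11-646) and 41.4% (Study M13-098), both non-cirrhotic populations. This trial sets no target.
- RBV-free subjects have no RBV dose modification, by definition.

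**Step 1: dilution of an RBV-specific percentage**

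RBV-free = (600 − F4) × b. Dilution factor = 1 − RBV-free / 600. Printed rate = rate among recipients × factor.

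| F4 | b | RBV-free | Share of 600 | On RBV | Factor | A 10% rate prints as |
|---|---|---|---|---|---|---|
| 150 | 32.3% | 145.35 | 24.2% | 454.65 | 0.758 | 7.58% |
| 100 | 32.3% | 161.5 | 26.9% | 438.5 | 0.731 | 7.31% |
| 150 | 41.4% | 186.3 | 31.1% | 413.7 | 0.690 | 6.90% |
| 100 | 41.4% | 207 | 34.5% | 393 | 0.655 | 6.55% |

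**Step 2: pooled hemoglobin below 10 g/dL**

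Rates are from protocol Table 3: 0% without RBV, 5.74% for GT1a non-cirrhotic subjects, 7.2% for GT1b cirrhotic subjects (12 weeks) and 11.0% for GT1a cirrhotic subjects (24 weeks). Two further assumptions are that b is the same in cirrhotic subjects and that all GT1a cirrhotic subjects take 24 weeks.

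Events = (600 − F4)(1 − b) × 5.74% + F4 × b × 7.2% + F4 × (1 − b) × 11.0%.

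- F4 = 100, b = 41.4%: 293 × 5.74% + 41.4 × 7.2% + 58.6 × 11.0% = 16.82 + 2.98 + 6.45 = 26.25. Pooled: 26.25 / 600 = 4.4%. RBV recipients: 26.25 / 393 = 6.7%.
- F4 = 150, b = 32.3%: 304.65 × 5.74% + 48.45 × 7.2% + 101.55 × 11.0% = 17.49 + 3.49 + 11.17 = 32.15. Pooled: 32.15 / 600 = 5.4%. RBV recipients: 32.15 / 454.65 = 7.1%.

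The pooled column would thus show about 4.4-5.4%, where the regimens run from 0% to 11.0%.

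All GT1a cirrhotic subjects on 24 weeks is the extreme case. At the other extreme, all take 12 weeks, and the same two corners give (16.82 + 100 × 7.2%) / 600 = 4.0% and (17.49 + 150 × 7.2%) / 600 = 4.7%. Among recipients they give 24.02 / 393 = 6.1% and 28.29 / 454.65 = 6.2%. The gap between pooled and recipient rates remains.

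**Step 3: does the direction hold generally?**

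It does not. In protocol Tables 2 and 3:
- ALT above 5 × ULN was 0% at 24 weeks and 0.2-2.9% in the other active groups, so pooling would overstate the 24-week figure.
- In the regimen-controlled studies, without versus with RBV, diarrhea was 11.4% versus 8.7% and headache 25.1% versus 24.4%.
- Among cirrhotic subjects, 24 versus 12 weeks, serious adverse events were 4.7% versus 6.3% and bilirubin above 3 × ULN was 5.2% versus 13.5%.

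**The case against.** The single column is deliberate. SAP 10.1 explains that it represents the treatment as labelled, the study is single-arm and descriptive, and safety is in no primary or secondary objective. A pooled rate misleads only if read as the rate of one regimen. That reason is given for efficacy, however, and it does not give meaning to an RBV dose-change percentage in subjects without RBV. Even for efficacy, Section 10.5 splits SVR12 by subtype and cirrhosis, and by duration in GT1 non-b subjects with cirrhosis.

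Three further points stand and limit the concern.

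- The RBV list in Section 8.0 has its own lead-in with no denominator. The safety population is named only for the section's first list. Dilution there is the default reading and not a stated rule; in 11.2.1.1 it follows more directly.
- Much can be recovered. Counts accompany the percentages, so a reader who knows the number given RBV can redo the division. Listings cover Grade 2 or worse hemoglobin and Grade 3 or worse liver tests, and Protocol 8.1.4.1 and 8.1.4.2 allow further analyses. A display chosen after the data are seen is nevertheless weaker than a planned one.
- Regimen is determined by subtype and cirrhosis, so regimen columns would describe and could not compare. Phase 3 already supplies by-regimen safety, including 172 subjects on 24 weeks, against roughly 59-102 here if all GT1a cirrhotic subjects take 24 weeks.

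A reader might infer that pooling makes every regimen's toxicity unreadable, or that it always understates 24-week toxicity and overstates RBV-free toxicity. The documents support neither: the listings, exposure categories and RBV compliance contradict the first, and Step 3 contradicts the second. Nor does the protocol say that its Phase 3 tables are split by regimen because rates differ; the split follows the source studies' designs.

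**Conclusion.** The point holds as a gap in the planned displays. Following SAP 11.2.1.1 as written, and Section 8.0 on its default reading, understates RBV dose-modification rates among those at risk. The printed figure would be about 0.65 to 0.76 of the rate among recipients, given 100-150 F4 subjects and an assumed GT1b share of 32.3-41.4% among non-cirrhotic subjects. The direction holds whenever any GT1b non-cirrhotic subject is enrolled; the size depends on a mix the trial does not fix.

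For anemia, the pooled column would sit at about half or less of the 24-week rate, if Phase 3 rates carry over. For other events the effect of pooling can go either way.

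A reader might also take this as a conflict between protocol and SAP. It is not one: Protocol 8.1.4 promises no safety tables by regimen.

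**What to change.** 1. In SAP 8.0 and 11.2.1.1, state that every RBV dose-modification percentage, including interruptions and adverse events leading to modification, uses as its denominator subjects who received at least one dose of RBV.
2. In SAP Section 11, show the key safety tables (adverse-event overview, common events, hemoglobin and liver-test grades) in three columns beside the total: 3-DAA 12 weeks, 3-DAA + RBV 12 weeks, and 3-DAA + RBV 24 weeks. State which column takes a subject whose treatment was extended after an initial 12-week assignment. Label the columns descriptive, since regimen is set by subtype and cirrhosis.

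The cost is a few lines of SAP text and extra table columns; the data are already collected. The downside is smaller denominators per column, most of all for 24 weeks.
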